### **3.1. Duration of Study**

This study should be completed within 24 months of the start date. Each patient will participate in the study for about 2 to 6 months.

### **3.3 Sample Size Justification**

We will recruit up to 10 patients for MASL treatment and 10 patients for placebo treatment to attempt a p value of less than 0.05 based on a difference of 40% with respect to Podoplanin expression and MASL sensitivity. Patients will be selected for treatment with MASL versus placebo by 1:1 randomization.

### **3.4 Subject Selection and Enrollment Considerations**

Subjects will be enrolled to fulfill a sample size in light of power considerations. These subjects will be enrolled from a well-defined population of patients presenting oral cancer or suspected lesions determined and treated by best care practice, and methods assuring human subjects' protections, including their voluntary & informed consent, privacy of person and confidentiality of data, and equitable access to research.

#### **3.5.1 Inclusion Criteria**

- 1.) Males and females of at least 18 years of age who are able to give consent.
- 2.) Smokers and non-smokers.
- 3.) Persons with white or red spots and/or lesions suspected or found to be oral cancer or precancer on the inner surface of the mouth.
- 4.) Oral lesions will be classified as OSCC or leukoplakia including, proliferative verrucous leukoplakia, conventional erythroplakia, suspect oral papillomas, or oral lichen planus. Only patients with such histologically confirmed diagnoses will be considered for inclusion.
- 5.) patients will be considered for inclusion at any stage of disease progression.
- 6.) Patients will be considered for inclusion if a subsequent biopsy or surgical resection are planned as part of their best care treatment.
- 7.) Patients with previously diagnosed oral cancer/precancer who present to the study clinicians for definitive surgical care, consent to participate, and meet the criteria for enrolment.
- 8.) Patients will have an Eastern Cooperative Oncology Group performance status of 0 or 1.
- 9.) Patients will display normal organ function as evidenced by standard laboratory blood tests including liver enzymes and creatine.
- 10.) Patients will not present evidence of comorbidities including ongoing or active infection, unstable illness, or medical conditions.

#### **3.5.2 Exclusion Criteria**

- 1.) Patients with cognitive impairments and cannot consent for themselves.
- 2.) Patients with language/hearing impairments.
- 3.) Use of a topical steroid product within the last 2 weeks.
- 4.) Pregnant women (to avoid any potential risk to the fetus) to be confirmed by standard blood or urine tests according to best care practice.
- 5.) Patients who are breastfeeding.
- 6.) Abstinence or use of adequate contraception will be required for women of childbearing potential and men of reproductive potential.

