### 1.3 Primary, Secondary, and Tertiary Endpoints

Endpoints will be determined by cell morphology and PDPN expression examined by IHC. This work will be performed as an integral part of the study. The protocols rely on standard staining protocols to visual cells and PDPN expression with an approved antibody (D2-40). We have experience with this approach as previously described [56].

Our primary endpoint will be measured from patient biopsy material. We will compare the morphology and PDPN expression of cells included in the oral lesion to normal oral squamous epithelial cells. Patients eligible for the study will provide samples with lesion cells that are determined to be OSCC and express more PDPN than normal cells from the same sample specimen. In addition, these OSCC cells will express PDPN levels that are equivalent or greater than PDPN levels expressed by lymphatic endothelial cells (LECs) from the same specimen. Although this may be considered inclusion criteria, it is also an endpoint since these data will confirm that PDPN expression is increased in OSCC cells in our patient population. PDPN expression will be assessed by IHC for this endpoint since it can be used to qualitatively and quantitatively assess PDPN expression and be accomplished along with standard evaluations used for best care practice.

Our secondary endpoint will be measured from patient resection or second biopsy material. We will compare the PDPN expression of cells included in the oral lesion to normal oral squamous epithelial cells. Our secondary endpoint will be met if MASL treated OSCC cells express less PDPN than normal cells from the same sample specimen. In addition, these OSCC cells will express PDPN levels that are lower than PDPN levels expressed by lymphatic endothelial cells (LECs) from the same specimen. Our secondary endpoint will also require that the degree of PDPN expression decrease occurring after MASL administration is greater than any PDPN expression decrease observed after placebo administration. This comparison will be analyzed by t-test to achieve a p value less than 0.05.

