In addition to the process described above, patients already diagnosed with oral cancer/precancer who present to one of the study clinicians for definitive care may also be enrolled in the study if they consent to participation. In these situations, it is routine to request H&E-stained slides from the original surgical pathology department for review as part of the surgical planning for clinical care. For patients who consent, the study clinician or PI would also request 1-3 unstained specimens for D2-40 staining to determine PDPN expression for research purposes. Patients with OSCC cells that express robust levels of PDPN and meet the eligibility criteria will be considered for treatment phase. The remainder of the protocol remains the same.

MASL and placebo lozenges will be prepared by an approved GMP certified facility by chromatography methods established by [name] as described [57]. Lozenges will be stored at the University Hospital Pharmacy and be hand delivered to the administering doctor by study investigators listed on page 1 in a sealed plastic container labeled with the patients name and ID. This work will be performed at the NJMS/RSDM/Rutgers Dental associates and University Hospital in Newark, NJ. [name], [name], [name], [name], [name] or [name] along with [name] and [name] will perform a general physical evaluation of their respective patients before and after MASL or placebo administration. [name] or [name] will

evaluate patient vital signs including temperature, pulse, blood pressure, and overall health after administration. [name] or [name] will also assist with management of any complication should it arise.

In this approach, MASL will find administration through topical exposure to oral lesions in the mouth as the lozenge dissolves. Patients will be asked to dissolve the lozenge in their mouth for at least 5 minutes before being chewed, and refrain from spitting, eating, or drinking for at least 20 minutes after lozenge administration. Subjects will be asked to finish chewing the lozenge within 20 minutes. Systemic exposure through the blood stream may also be accomplished. Data from university studies on cell lines and animal models indicate that MASL can be applied topically or eaten to target PDPN in order to inhibit tumor cell growth and migration. However, pharmacokinetics of this compound have not been established.

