## Schedule of Events

Subject Recruitment	
Identification of patients with premalignant or malignant lesions during the course of clinical care (this includes previously diagnosed oral cancer/precancer patients presenting for surgical resection as part of clinical care)	[name] [name] [name] [name]
informed consent	[name] [name]
Clinical procedures as per best care practice	
Diagnostic tissue biopsy	[name] [name] [name] [name] [name] [name]
Laboratory Procedures	
Diagnostic histopathology, Evaluation of cell morphology & PDPN expression	[name] [name]
Identification of patient samples with robust PDPN expression	
Clinical procedures as per best care practice	
Planning resection or second biopsy	[name] [name] [name] [name] [name] [name]
Treatment Phase	
Evaluation of eligibility criteria for enrolment. Eligible patients: 
 
• Have tissue samples with robust PDPN expression
 
• Have not used topical steroid products within the last 2 weeks
 
• Have Eastern Cooperative Oncology Group performance status of 0 or 1.
 
• Display normal organ function as evidenced by standard laboratory blood tests including liver enzymes and creatine.
 
• Do not present evidence of comorbidities including ongoing or active infection, unstable illness, or medical conditions.
 
• Not pregnant as per standard blood or urine tests according to best care practice
 
• Not breast feeding
 
• Consent to Abstinence or use of adequate contraception (women of childbearing potential and men of reproductive potential)
 
	[name] [name] [name] [name] [name] [name]
MASL administration within 1 week of planned biopsy or resection	[name] [name] [name] [name] [name] [name] [name] [name]
Clinical procedures as per best care practice	
Planned resection or second biopsy	[name] [name] [name] [name] [name] [name]
Laboratory Procedures	
Diagnostic histopathology, Evaluation of cell morphology & PDPN expression	[name] [name]

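### The steroid check does not cover the baseline specimen and no criterion covers anticancer therapy before the lozenge: direct bias for the tertiary dysplasia rule, mainly lost precision for the placebo-compared PDPN decrease

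*Protocol*

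**What the plan says.** The only medication exclusion in Protocol section 3.5.2 is "Use of a topical steroid product within the last 2 weeks". The section does not say what the two weeks are counted back from. The Schedule of Events places the check in the treatment phase ("Have not used topical steroid products within the last 2 weeks"), below the diagnostic biopsy and its PDPN staining. The lozenge is then given within one week of the planned second biopsy or resection.

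Section 3 adds a second way in: "patients already diagnosed with oral cancer/precancer who present to one of the study clinicians for definitive care may also be enrolled". Their PDPN status is read from unstained material requested from the original pathology department, with no limit on its age. Section 3.5.1 says that "patients will be considered for inclusion at any stage of disease progression". Neither 3.5.1 nor 3.5.2 mentions radiotherapy, chemotherapy or other systemic anticancer therapy.

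The secondary endpoint in section 1.3 has three conditions. Two compare lesion cells with normal cells and with lymphatic endothelial cells inside the second specimen. The third requires that "the degree of PDPN expression decrease occurring after MASL administration is greater than any PDPN expression decrease observed after placebo administration", and "This comparison will be analyzed by t-test to achieve a p value less than 0.05". The tertiary endpoint is met if MASL-treated cells look less dysplastic than before treatment; the rule has no placebo term.

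Section 6 says that patients receive no other drugs or devices. Section 4.3 says that they are treated according to standard care, and section 3 that participation should not affect their treatment.

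**The concern.** A before/after comparison needs to know what else happened to the lesion between the two specimens. The protocol recognises this for topical steroid, but ties the check to a date on which neither specimen is taken. A patient can be on topical steroid at the first biopsy, off it for two weeks at eligibility, and so enter with one specimen on steroid and one off. A previously diagnosed patient can have had anticancer therapy after the outside biopsy and meet every listed criterion.

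Three things are at stake: whether a dysplasia improvement in the MASL arm can be credited to the lozenge, how much precision the PDPN comparison keeps with 10 patients per arm, and whether the PDPN threshold that opens the treatment phase describes the lesion as it stands when the patient is randomised.

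**Working it through.** **Which comparisons are exposed.**

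| Element (section 1.3) | Uses the baseline specimen | Compared with placebo |
|---|---|---|
| Secondary: lesion vs normal and lymphatic endothelial cells | No (second specimen only) | No |
| Secondary: PDPN decrease | Yes | Yes, randomised 1:1 |
| Tertiary: dysplasia change | Yes | No |
| PDPN threshold for treatment (also section 3) | Yes | Not applicable |

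**The plan's own figure.** Section 3.3 says "We will recruit up to 10 patients for MASL treatment and 10 patients for placebo treatment", for p < 0.05 on a 40% difference. It gives no SD, power or scale, so 10 per arm can be neither reproduced nor refuted. Reading 40% as 40 points with a two-sided t-test, 10 per arm gives 80% power at a standardised difference of 1.325, that is SD = 40/1.325 = 30, and 90% power at 1.534, SD = 40/1.534 = 26. Power is 99% at SD 20, 56% at SD 40 and 29% at SD 60. SD 30 is used below as an assumption.

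**Secondary PDPN decrease, exposure before randomisation.** Assume that exposure lowers PDPN by e points in k of 20 patients, split 10:10 at random. With e = 40 and SD 30 (40,000 simulated trials):

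| Exposed (k of 20) | False-positive rate, no MASL effect | Power, true 40-point effect |
|---|---|---|
| 0 | 4.9% | 81% |
| 4 | 5.1% | 69% |
| 8 | 5.2% | 65% |

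The mean between-arm difference with no MASL effect is about 0 in each row. The power loss follows from the added variance p(1−p)e², with p = k/20. For k = 4 it is 0.2 × 0.8 × 1600 = 256, so SD = √(900 + 256) = 34. For k = 8 it is 0.4 × 0.6 × 1600 = 384, so SD = √1284 = 35.8.

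Over a range of e, using normal-theory t-test power of 81% at SD 30, 75% at SD 32, 56% at SD 40 and 40% at SD 50 (rough for large e):
- e = 20: SD = √(900 + 64) = 31.0 for k = 4 and √(900 + 96) = 31.6 for k = 8; power 75% to 81%.
- e = 80: SD = √(900 + 1024) = 43.9 for k = 4 and √(900 + 1536) = 49.4 for k = 8; power 40% to 56%.

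Chance imbalance is common. With 4 exposed, the arms differ by 2 or more patients with probability 1 − C(10,2)²/C(20,4) = 1 − 2025/4845 = 0.58. All 4 fall in one arm with probability 2 × 210/4845 = 0.087. With 8 exposed, a difference of 4 or more has probability 0.17.

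**Before/after reading in the MASL arm only.** The expected false change is (k/20) × e. With e = 40 this is 8 points for k = 4 and 16 points for k = 8. Over e = 20 to 80 it is 4 to 16 points for k = 4 and 8 to 32 points for k = 8. With e = 40 and SD 30, a one-sample t-test declares a decrease in 2.5%, 8.2% and 21.9% of simulated trials for k = 0, 4 and 8. Dysplasia is graded 1 to 5 and section 1.3 names no test for it, so these rates show the mechanism, at an exposure effect of 40/30 = 1.33 SD. They are not a forecast for that scale.

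**Treatment threshold.** Section 3 judges PDPN on the first specimen. If that specimen was taken on steroid, or before anticancer therapy, it may not describe the lesion at randomisation.

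**The case against.** The strongest reply is that the PDPN decrease is tested against randomised placebo, with pathologists blinded to arm. A reader might infer that steroid or therapy before randomisation would be read as a MASL effect on PDPN, or that one or two such patients could create a significant difference. The documents do not support that. Such exposure is balanced in expectation, and chance imbalance is already inside the t-test's error rate, as the simulation shows. This objection stands and limits the secondary-endpoint point to lost power. One route to bias remains: clinicians who give the lozenge are unblinded and the time of randomisation is not fixed, so therapy after allocation could differ by arm.

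A reader might also take "Each patient will participate in the study for about 2 to 6 months" as the gap between specimens. It is total time on study. Lozenge to second specimen is limited to one week; first specimen to lozenge is not limited.

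The steroid route is doubtful for lichen planus or leukoplakia patients. Section 3.5.1 lists these lesions, but sections 1.3 and 3 speak of treating patients whose OSCC cells express robust PDPN. The outside-tissue and anticancer-therapy routes are the firmer ones.

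The protocol also documents no effect of topical steroid or anticancer therapy on PDPN or dysplasia, and none in a known direction. Section 2 says only that EGF signalling can induce PDPN in OSCC cell lines. This stands: size, direction and number exposed are all unknown. Treatment before surgery is nevertheless foreseeable, since the bibliography lists a study of podoplanin in OSCC after neoadjuvant radiochemotherapy.

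Finally, section 6 might seem to close the gap by saying that no other drugs are given. It cannot reach treatment before enrolment, and read literally it conflicts with the standard-care statements in sections 3 and 4.3.

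**Conclusion.** The point holds in limited form. The one washout is undated and checked after the baseline specimen, and therapy between that specimen and the lozenge is not addressed. Eligibility and the tertiary success rule are both fixed in the protocol, so this is not detail left to a later analysis plan.

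- **Tertiary endpoint:** direct bias, because randomisation plays no part in the rule.
- **Secondary PDPN decrease:** no expected bias from exposure before randomisation, but noise and chance imbalance that are costly at 10 per arm.
- **Treatment threshold:** possible misclassification, not quantifiable from the documents.

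The sizes rest on an assumed SD, exposure effect and number exposed, none of which the protocol gives. If no patient is exposed, none of them arises. The conclusion about where bias can enter rests on the design alone.

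**What to change.** 1. In section 3.5.2 and the Schedule of Events, date the existing two-week steroid criterion relative to the baseline specimen as well as treatment entry, using chart history for outside biopsies.
2. Make it an eligibility condition that no radiotherapy or systemic anticancer therapy fell between the baseline specimen and randomisation, so that the baseline reflects the lesion as randomised.
3. Record all steroid and anticancer exposure up to the second specimen without restricting care, and keep every randomised patient in the comparison.
4. Rewrite the tertiary rule in section 1.3 so that the dysplasia change after MASL is judged against the change after placebo. The placebo patients are already in the design.
5. Reconcile section 6 (no other drugs or devices) with sections 3 and 4.3 (standard care continues). Any limit on treatment after enrolment is for the sponsor to decide.

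The cost is protocol wording, a history check for each patient, which is more work for outside biopsies, and the loss of a few otherwise eligible patients.

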#### **3.5.3 Subject Recruitment**

Subjects will be recruited directly by [name], [name], [name], [name], [name] and [name]. Patients will be selected for treatment with MASL versus placebo by 1:1 randomization.

### **3.5.4 Consent Procedures**

The consent process will take place before the initiation of the study procedures. The physicians will discuss this process during the first office visit prior to surgery, or earlier. Patient will be approached with the forms and have the protocol described to them. Participants will discuss their participation with the surgeons before signing the consent form. A full description of the project will be given to the prospective participants in lay language in sufficient time for them to consider whether or not to participate in the study.

The entire process will be described to each subject in lay language in order for them to fully understand the nature of their involvement in the research. Consent will not be sought from subject with cognitive and/or language/hearing impairments as described in the experimental protocols.

### **3.5.5 Subject Costs and Compensation**

There will be no costs or compensation for participants. This work will utilize samples to be taken during the course of standard care.

### **3.6 Chart Review Selection**

All study documents such as consent forms, biopsy reports, and patient's identifiers (name, gender, birth date, etc.) are maintained in a locked cabinet in the PI's office ([name]) in Newark. A copy of the relevant data (name, gender, DOB,..) including biopsy reports will also be kept in [name] office in the science center at SOM. This information will not be transferred to any files used for tissue analysis or other procedures. These identifiers will only be accessible to cross referencing a coded sample number that is used for all research purposes. Patient identifiers will only be used to verify results with the physicians that are involved in this study.

## **4. Study Variables**

### **4.1 Independent Variables or Interventions**

#### **4.1.1 Drug or Device Interventions**

This study involves the potential drug MASL (FDA IND#: 118210). MASL will be extracted, purified, and compounded into lozenges by the University of California GMP facility by protocols that result in MASL that is essentially free of salts and other contaminants that can be successfully used in cell culture and animals [57,56]. Patients will be given a lozenge with or without MASL added to achieve a final dosage of 100 mg per adult. Patients will be given a lozenge with or without MASL added to achieve a final dosage of 100 mg per adult. MASL will be prepared by the University of California Davis GMP facility. Patients will be watched for 2 hours after administration and examined for any reactions to the treatment.

As described above (see Section 3) MASL targets PDPN to inhibit tumor cell growth and motility [1,38,57]. Although some lectins may nonspecifically bind to many glycoproteins, MASL can precisely target specific glycoproteins expressed by human cells [47,46]. MASL can be taken

orally to inhibit tumor growth in mice. Moreover, no side effects were evident from MASL ingestion based on animal weight, behavior, or organ morphology [57,65]. Human safety for MASL has already been demonstrated as a “coincidental” component in traditional medicines used to treat ailments including cancer. *Maackia amurensis* has been used as a medicinal plant in Asia for several centuries, with doses averaging 100 mg per adult administration [43,45,42,44,13]. However, human safety studies for MASL have not been reported.

#### **4.2 Dependent Variables or Outcome Measures**

Up to 1 gram of tumor tissue will be analyzed. The cells in this tissue will be adapted to cell culture. Protein will be examined by IHC and Western blotting. Effects of MASL on PDPN expression, cell growth, migration, and morphology will be analyzed by standard growth, motility, and IHC assays. Patient age and sex will be correlated to these results to determine if correlations exist between age and sex.

#### **4.3 Risk of Harm**

Some medical risks are associated with this study since patients will be treated according to standard care and with an experimental nutraceutical (MASL). This compound has been used as an anecdotal incidental component of traditional medicines for many centuries without reports of harmful side effects. Risks of information distribution would involve patient name, age, sex, and tumor grade. These risks will be minimized by keeping information related to patient identifiers encoded, locked in the PI’s office, password protected, and destroyed after the study. Patient specimens will not be labeled with patient names or other identifiers; they will be labeled with unique identifiers to maintain patient privacy and confidentiality.

Protocols are in place for assessment and treatment of potential reactions to MASL. Patients will be observed for 2 hours after every administration for any development of effect such as hypersensitivity reaction. Any individual who develops suspected allergic episode will be evaluated for manifestations such as urticaria, angioedema, flushing, pruritus, upper airway obstruction, gastrointestinal symptoms, syncope, hypotension, and lower airway obstruction. Mild allergic reactions will be treated with anti-histamines and/or epinephrine. If the patient has moderate to severe anaphylaxis, intramuscular epinephrine will be administered into the lateral thigh. The adult dose of 1:1,000 epinephrine is 0.2 to 0.5 mL. If there is no significant improvement in symptoms, then the dose will be repeated approximately every 5 to 15 minutes, as the physician deems to be necessary. Intravenous or oral corticosteroid 1 to 2 mg/kg per dose up to 125 mg of methylprednisolone will be considered to decrease the biphasic or prolonged reactions. If needed, oxygen up to 100% will be administered at a flow rate of 6 to 10 L/min through a facemask. Oxygen saturation will be monitored and kept at 94% to 96% by oximetry. For signs and symptoms of bronchospasm (eg, wheezing, coughing, and shortness of breath) that has not responded to intramuscular epinephrine, albuterol will be administered through a nebulizer and facemask. Hypotension will be treated with rapid fluid replacement using 1 to 2 L of 0.9% normal saline, infused rapidly. For the normotensive patient in anaphylaxis, starting normal saline at an appropriate maintenance rate for weight (125 mL/h for adults) to maintain venous access for medications and/or rapid fluid replacement will be considered if necessary.

If the patient has severe anaphylaxis or is showing signs and symptoms of impending cardiopulmonary arrest, EMS will be summoned immediately in addition to all available office medical staff. Cardiopulmonary resuscitation will be started immediately in the event of cardiopulmonary arrest, with emphasis on adequate chest compressions without interruption.

Ventilations can be given once there are 2 medical staff members at the patient's side. For imminent or established cardiopulmonary arrest, venous access will be rapidly established to administer an intravenous bolus dose of epinephrine. For adults, the dose is 1 mg intravenously as a 1: 10,000 dilution that can be repeated every 3 to 5 minutes. If epinephrine is ineffective in treating anaphylaxis in patients taking b-blockers, then glucagon administration might be necessary.

Patient's blood pressure, cardiac rate and function, respiratory status, and oxygenation will be monitored and recorded at frequent and regular intervals. The duration of direct observation and monitoring after an episode of anaphylaxis will be individualized and based on the severity and duration of the anaphylactic event and response to treatment. Patients with moderate to severe anaphylaxis will be observed for a minimum of 4 to 8 hours. Mild anaphylactic symptoms that rapidly resolve with treatment usually will require a relatively shorter period of observation. At the time of discharge from medical supervision, patients will be instructed to call the office or call 911 or go to the emergency room in case there is recurrence of symptoms of an allergic reaction. Prescription, written action plan and follow up visits deemed necessary will be discussed upon discharge.

